5.3. Handling of Missing Data

In general, analysis will be performed on all available data and no imputation will be performed for missing data. However, if there are withdrawals from study treatment due to issues pertaining to the use of the safety syringe, sensitivity analysis of the primary endpoint will be performed, as described in Section 7.1.

5.4. Data Display Standards

5.4.1. Study Treatment Descriptors

RandAll NG		Data Displays for Reporting	
Code	Description	Description	Order
	Not applicable	Liquid Safety Syringe	1

5.4.2. Sub-group Display Descriptors

Data Displays for Reporting		
Subgroup Descriptor	Category	Order
Baseline Mepolizumab Use	No	1
	Yes	2
Injection Site	Abdomen	1
	Upper Arm	2
	Thigh	3

5.5. Other Considerations for Data Analysis and Data Handling Conventions

Table 1 provides an overview of the appendices within the RAP for outlining other general considerations for data analyses and data handling conventions.

Table 1 Overview of Appendices

Section	Component
Section 14.1	Appendix 1: Time & Events
Section 14.2	Appendix 2: Treatment States and Phases 
 • Treatment Phases for Adverse Events • Treatment Phases for Exacerbations
Section 14.3	Appendix 3: Data Handling Conventions 
 • Baseline Definition & Derivations • Reporting Process & Standards
Section 14.4	Appendix 4: Derived and Transformed Data 
 • General, Study Population & Safety
Section 14.5	Appendix 5: Premature Withdrawals & Handling of Missing Data 
 • Premature Withdrawals • Handling of Missing Data • Handling of Missing and Partial Dates
Section 14.6	Appendix 6: Values of Potential Clinical Importance

6. STUDY POPULATION ANALYSES

The study population analyses will be based on the “All Subjects (Safety)” population.

6.1. Overview of Planned Analyses

Table 2 provides an overview of the planned study population analyses. Full details of the data displays to be presented are given in Appendix 8: List of Data Displays.

Table 2 Overview of Planned Study Population Analyses

Display Type	Data Displays Generated		
	Table	Figure	Listing
Study Populations	Y		Y
Screen Failures	Y		Y
Treatment Discontinuation	Y		Y
Subject Disposition	Y		Y
Important Protocol Deviations	Y		Y
Exposure to Study Treatment	Y		Y
Inclusion/Exclusion Deviations			Y
Demographics	Y		Y
Disease Duration	Y		
Baseline Mepolizumab Use	Y		Y
Prior Experience with Self-Injection	Y		
Past and Current Medical Conditions	Y		Y
Family History of Cardiovascular Risk Factors	Y		Y
Other Family History			Y
Smoking History	Y		
Concomitant Medications			Y

NOTES :

- Y = Yes display generated.

7. ANALYSES TO EVALUATE SAFETY SYRINGE

All analyses will be based on the “All Subjects (Safety)” population.

7.1. Overview of Planned Primary Analyses

The primary endpoint is the proportion of subjects successfully able to self-administer their observed third dose at Week 8.

- The number and percentage of subjects successfully able to self-administer their observed third dose at Week 8 will be summarized together with 95% CI.
- The denominator for the percentage calculation will be the number of subjects attempting an injection at Week 8.
- CI for the percentages will be generated using the Exact (Clopper-Pearson) method for binomial proportions.
- No formal statistical analysis will be conducted.
- If there are withdrawals from study treatment due to issues pertaining to the use of the safety syringe, a sensitivity analysis of the primary endpoint will be performed. Missing injection success assessments following withdrawal from study treatment due to issues with the safety syringe will be included in the analysis as injection failures i.e. unsuccessful attempts to self-administer mepolizumab. Injection success assessments classed as “not attempted” on the eCRF following withdrawal from study treatment due to issues with the safety syringe will also be included in this analysis as injection failures.

Table 3 provides an overview of the planned analysis of the primary endpoint, with full details of data displays being presented in Appendix 8: List of Data Displays.

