5.6. Subject and Study Completion

A completed subject is one who has completed the End of Study (Week 12) visit.

The end of the study is defined as the last subject's last visit.

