6.6. Preparation/Handling/Storage/Accountability

No special preparation of study treatment is required.

Study treatment must be dispensed or administered according to procedures described herein. Only subjects enrolled in the study may receive study treatment. Only authorised site staff may supply study treatment. All study treatment must be stored in a secure area with access limited to the investigator and authorised site staff.

Mepolizumab will be supplied in a single-use safety syringe and should be stored in a refrigerator at 2 to 8°C with protection from light. Each injection device will contain 100 mg mepolizumab as a single 1.0 mL injection of the liquid drug product (100 mg/mL). Maintenance of a temperature log at the clinical dispensing sites (manual or automated) is required.

- The investigator or designee must confirm appropriate temperature conditions have been maintained during transit for all study treatment received and any discrepancies are reported and resolved before use of the study treatment.
- Only the subject or previously identified caregiver may administer the study treatment. Whilst on site, all study treatments must be stored in a secure environmentally controlled and monitored (manual or automated) area in accordance with the labelled storage conditions with access limited to the investigator and authorised site staff.
- The investigator, institution, or the head of the medical institution (where applicable) is responsible for study treatment accountability, reconciliation, and record maintenance (i.e. receipt, reconciliation and final disposition records).
- Further guidance and information for final disposition of unused study treatment are provided in the SRM.
- Under normal conditions of handling and administration, study treatment is not expected to pose significant safety risks to site staff.

- A Material Safety Data Sheet (MSDS)/equivalent document describing occupational hazards and recommended handling precautions either will be provided to the investigator, where this is required by local laws, or is available upon request from GSK.

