9.4. Key Elements of Analysis Plan

9.4.1. Analyses to Evaluate Safety Syringe

Primary Endpoint

The number and percentage of subjects successfully able to self-administer their observed third dose at Week 8 will be summarized together with 95% confidence intervals. The denominator for the percentage calculation will be the number of subjects attempting an injection at Week 8.

Secondary Endpoints

The following will be summarized, including 95% CIs:-

- The number and percentage of subjects successfully able to self-administer their unobserved second dose at Week 4. The denominator for the percentage calculation will be the number of subjects attempting an injection at Week 4.
- The number and percentage of subjects successfully able to self-administer their observed first dose at Week 0. The denominator for the percentage calculation will be the number of subjects attempting an injection at Week 0.
- The number and percentage of subjects successfully able to self-administer both their unobserved second dose at Week 4 and their observed third dose at Week 8. The denominator for the percentage calculation will be the number of subjects attempting an injection at both Week 4 and Week 8.
- The number and percentage of subjects successfully able to self-administer all three doses at Week 0, 4 and 8. The denominator for the percentage calculation will be the number of subjects attempting all 3 doses at Week 0, 4 and 8.

Data collected on the Observation Checklist relating to the correct use of the safety syringe and any device related issues preventing the full dose being administered will be summarised at each visit.

The root cause evaluation of each unsuccessful injection via the Safety Syringe Error/Failure Reporting Form, including any observations noted by GSK Device Engineering, will be summarized separately by GSK Device Engineering for inclusion into the study report.

Device usability/functionality assessed at the end of the study will be summarised.

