14.5.2. Handling of Missing Data

Element	Reporting Detail
General	
 • In general, analysis will be performed on all available data and no imputation will be performed for missing data. However, if there are withdrawals from the study due to issues pertaining to the use of the safety syringe, a sensitivity analysis of the primary analysis will be performed. Missing or “not attempted” injection success assessments following these withdrawals will be imputed as injection failures i.e. unsuccessful attempts to self-administer mepolizumab in this sensitivity analysis. • Missing data occurs when any requested data is not provided, leading to blank fields on the collection instrument. These data will be indicated by the use of a “blank” in subject listing displays, unless all data for a specific visit are missing in which case the data is excluded from the listing. • Data below the limit of quantification (BLQ) is not missing data and must be displayed as such and included in all listings and summaries.
Outliers	
 • Any subjects excluded from the summaries and/or statistical analyses because their values are considered outliers will be documented along with the reason for exclusion in the clinical study report.

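### A Week 8 non-attempt counts as a failure only after a withdrawal due to syringe issues, so other use-related non-attempts can be missing from every planned success proportion

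*SAP*

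**What the plan says.** Protocol 9.4.1 and SAP 7.1 give the same primary denominator: "The denominator for the percentage calculation will be the number of subjects attempting an injection at Week 8". The general rule for missing data, in SAP 5.3, is: "In general, analysis will be performed on all available data and no imputation will be performed for missing data".

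The one exception is the sensitivity analysis in SAP 7.1, which is conditional: "If there are withdrawals from study treatment due to issues pertaining to the use of the safety syringe, a sensitivity analysis of the primary endpoint". Two imputation rules follow, and each carries the same condition. For missing results: "Missing injection success assessments following withdrawal from study treatment due to issues with the safety syringe will be included in the analysis as injection failures". For results recorded as not attempted: those "on the eCRF following withdrawal from study treatment due to issues with the safety syringe will also be included in this analysis as injection failures". SAP 14.5.2 repeats the arrangement with a different trigger, "if there are withdrawals from the study due to issues pertaining to the use of the safety syringe", whereas SAP 5.3 and 7.1 refer to withdrawal from study treatment.

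On completion, Protocol 5.6 states: "A completed subject is one who has completed the End of Study (Week 12) visit". Protocol 4.2 also expects adherence to the treatment and assessment schedule. Protocol 4.2 and 5.5 both withdraw from the study a subject who permanently stops study treatment.

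**The concern.** The SAP accepts that not attempting an injection can be a failure of use, because it imputes failure after syringe-related withdrawals. That protection depends on two things: a withdrawal must be recorded, and it must be attributed to the syringe. No rule says which recorded reasons qualify or who decides.

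The study is descriptive, with no hypothesis test, so the proportion and its interval are the whole primary result. If people who have used the syringe and will not use it again fall outside the attempt-based denominator and also outside the sensitivity analysis, the result overstates how many can self-administer repeatedly. Deciding attribution after the data are seen, in an open-label study, would also be open to challenge.

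**Working it through.** **1. Which Week 8 outcomes reach a planned success proportion**

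| Situation at Week 8 | Primary analysis | Sensitivity analysis |
|---|---|---|
| Attempts and succeeds | success | success |
| Attempts but misses a critical step | failure (Protocol 7.3) | failure |
| No attempt, after withdrawal attributed to syringe issues | excluded | failure |
| No attempt, after withdrawal under another reason | excluded | excluded, or analysis not run |
| No attempt at Visit 4, no withdrawal recorded | excluded | excluded, or analysis not run |

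The last two rows are the gap. The combined endpoints in SAP 7.2 (Weeks 4 and 8; Weeks 0, 4 and 8) also use attempters only, so they do not recover these subjects.

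**2. Can those two rows occur?**

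- *Another reason.* Protocol 5.5 allows withdrawal at the subject's own request, or at the investigator's discretion on safety, behavioural or administrative grounds. Protocol 5.5.1 lists withdrawal of consent and loss to follow-up. A subject who stops because of injection pain or reluctance to inject could be recorded under one of these or as an adverse event. This is the firmer route.
- *No withdrawal recorded.* Dose 3 is the last dose, and Protocol 5.6 ties completion to the Week 12 visit. Site staff cannot give a declined dose, because "Only the subject or previously identified caregiver may administer the study treatment". Shell TAB_INJ2 has a category for injections not attempted. This route is narrow, because Protocol 4.2 and 5.5 can be read as making a permanent refusal a withdrawal.

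**3. Reproducing the plan's own precision figure**

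Inputs: n = 50 (Protocol 9.2.2) and the exact Clopper-Pearson method (SAP 7.1). For x successes in n, the lower limit is the 0.025 quantile of Beta(x, n − x + 1) and the upper limit is the 0.975 quantile of Beta(x + 1, n − x). For x = 47 this gives 83.5% and 98.7%, which round to the 83 and 99 printed in the 94% row. All 11 rows of the table reproduce.

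**4. Size under assumed non-attempts**

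Protocol 9.2.1 plans 55 enrolled and at least 50 with complete data, allowing up to 10% dropout (55 × 0.9 = 49.5). Assumptions: 50 subjects attempt dose 3, 47 succeed, and k further subjects make no attempt without a withdrawal attributed to the syringe. Counting those k as failures gives 47/(50 + k).

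| k | Proportion | Exact 95% CI |
|---|---|---|
| 0 (as planned) | 47/50 = 94.0% | 83.5, 98.7 |
| 1 | 47/51 = 92.2% | 81.1, 97.8 |
| 2 | 47/52 = 90.4% | 79.0, 96.8 |
| 5 (worst case, 55 − 50) | 47/55 = 85.5% | 73.3, 93.5 |

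If no withdrawal is attributed to the syringe, the planned analyses report 94.0% in every row. At k = 5 the estimate differs by 94.0 − 85.5 = 8.5 points and the lower limit by 83.5 − 73.3 = 10.2 points, or 10.1 before rounding.

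The gap in the estimate at k = 5 depends little on the observed rate: 45/50 = 90.0% becomes 45/55 = 81.8% (8.2 points), and 50/50 = 100% becomes 50/55 = 90.9% (9.1 points).

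**The case against.** There is a serious case for the plan as written.

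- *Someone who tries and cannot inject is already a failure.* This stands. Protocol 7.3 treats a missed critical step as an unsuccessful injection, and the observer checklist covers tasks not completed or needing intervention. The gap is confined to subjects who make no attempt at all.
- *Refusing the last dose is permanent discontinuation.* This is a fair reading of Protocol 4.2 and 5.5. If the refusal is recorded that way and put down to the syringe, SAP 7.1 counts it. No text requires that recording, so the case is narrow but not closed.
- *SAP 7.1 is not tied to a reason code.* True. A needle stick or fear of injecting could be classed as a syringe issue. The supportable criticism is that no attribution rule is written, not that the analysis would necessarily miss such a subject.
- *Nothing is hidden.* Largely true. TAB_INJ1 prints N and the attempted number at each visit, TAB_INJ2 tabulates injections not attempted, and discontinuation reasons are summarised and listed. A reader could work out 47/55. No planned success proportion or interval does so, and the list of displays in SAP 14.8.2 has no entry for the sensitivity analysis itself.
- *Not every non-attempt is a use failure.* This stands. Withdrawal for pregnancy, QTc or liver stopping criteria says nothing about ability to use the syringe.

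**Conclusion.** The point holds in limited form. SAP 7.1 can leave use-related non-attempts out of every planned success proportion, mainly when a withdrawal is recorded under another reason and, more rarely, when no withdrawal is recorded. If that happens, the attempt-based estimate is too high and the sensitivity analysis would not show it.

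A reader might infer that the primary estimate is biased upward as a matter of fact, or that the safeguard fails in practice. The documents support neither. Direction and size depend on how many subjects do not attempt and why, and the documents give no such numbers. The illustration runs from about 2 points for one subject to 8.5 points for five, starting from 47/50. The latter assumes that every planned dropout is a failure. No success threshold is stated that a changed figure would cross.

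The difference in trigger wording has little analytic effect, because permanent withdrawal from treatment leads to withdrawal from the study. It is a matter of consistency.

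**What to change.** Keep the attempt-based proportion as the headline. Beside it, always report two further rows in TAB_INJ1, with exact intervals:

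- (a) The Week 8 proportion with every not-attempted record of a subject attending Visit 4 counted as a failure, with or without withdrawal.
- (b) A worst-case bound with the All Subjects (Safety) population as denominator, counting any missing or not-attempted Week 8 result as a failure whatever the reason. Label it as a bound, because some non-attempts are unrelated to use.

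Neither row needs a judgement on whether a withdrawal was due to the syringe. Amend SAP 5.3, 7.1 and 14.5.2 accordingly and use one trigger wording in all three.

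The cost is SAP text and two table rows from data already collected, with no change to conduct or to the primary endpoint. The downside is that the supplementary figures will be less favourable and the bound will count some unrelated dropouts as failures.

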7.2. Other Analyses to Evaluate Safety Syringe

The following endpoints will be summarised in the same way as the primary endpoint (Section 7.1).

- The number and percentage of subjects successfully able to self-administer their unobserved second dose at Week 4. The denominator for the percentage calculation will be the number of subjects attempting an injection at Week 4.
- The number and percentage of subjects successfully able to self-administer their observed first dose at Week 0. The denominator for the percentage calculation will be the number of subjects attempting an injection at Week 0.
- The number and percentage of subjects successfully able to self-administer both their unobserved second dose at Week 4 and their observed third dose at Week 8. The denominator for the percentage calculation will be the number of subjects attempting an injection at both Week 4 and Week 8.

- The number and percentage of subjects successfully able to self-administer all three doses at Week 0, 4 and 8. The denominator for the percentage calculation will be the number of subjects attempting all three doses at Week 0, 4 and 8.

Table 3 provides an overview of the analyses to evaluate the safety syringe, with full details of data displays being presented in Appendix 8: List of Data Displays.

Table 3 Overview of Analyses to Evaluate Safety Syringe

	Summary		Individual	
	T	F	F	L
Primary Endpoint				
Proportion of subjects successfully able to self-administer their observed third dose at Week 8.	Y			Y
Secondary Endpoint				
Proportion of subjects successfully able to self-administer their unobserved second dose at Week 4.	Y			Y
Other Endpoint				
Proportion of subjects successfully able to self-administer their observed first dose at Week 0.	Y			Y
Proportion of subjects successfully able to self-administer their unobserved second dose at Week 4 and their observed third dose at Week 8.	Y			Y
Proportion of subjects successfully able to self-administer all three doses at Week 0, 4 and 8.	Y			Y
Investigator assessment of user/device errors by visit	Y			Y
Observer checklist for in-clinic injections	Y			Y ¹
Subject completed checklist for home injection	Y			Y ¹
Device usability/functionality subject completed questionnaire	Y			

NOTES :

- T = Table, F = Figure, L = Listing, Y = Yes display generated.
- Summary = Represents TFL related to any summaries (i.e. descriptive statistics) of the observed raw data.
- Individual = Represents FL related to any displays of individual subject observed raw data.
- ¹ Listings will include person administering injection and time from removal of syringe from storage to injection only. Injection site will be included on the exposure listing (see Table 2).

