14.8.2. Evaluation of Safety Syringe

No.	Population	IDSL / TST ID / Example Shell	Title	Programming Notes	Deliverable [Priority]
Evaluation of Safety Syringe - Tables					
7.1	All Subjects	TAB_INJ1	Summary of the Proportion of Subjects Successfully Able to Self-Administer Injection by Visit		SAC
7.2	All Subjects	TAB_INJ2	Summary of Investigator Evaluation of User/Device Errors by Visit		SAC
7.3	All Subjects	TAB_INJ3	Summary of Observer Checklist for In-Clinic Injections		SAC
7.4	All Subjects	TAB_INJ4	Summary of Subject Completed Checklist for At-Home Injection at Week 4		SAC
7.5	All Subjects	TAB_INJ5	Summary of Device Usability/Functionality Questionnaire		SAC

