userid: /arenv/arprod/compound/study/final/drivers/drivername.sas DDMMYYYY HH:MM

Example TAB_INJ1
Protocol: MID205667
Population: All Subjects (Safety)

Table X
Summary of Proportion of Subjects Successfully Able to Self-Administer Injection by Visit

Visit	Liquid Safety Syringe (N = XX)		
	Attempted Injections	Successful Injections [1]	
	n (%)	n (%)	95% CI
WEEK 0	XX (XX%)	XX (XX%)	(XX%, XX%)
WEEK 4	XX (XX%)	XX (XX%)	(XX%, XX%)
WEEK 8	XX (XX%)	XX (XX%)	(XX%, XX%)
WEEK 4 and 8	XX (XX%)	XX (XX%)	(XX%, XX%)
WEEK 0, 4 and 8	XX (XX%)	XX (XX%)	(XX%, XX%)

[1] The denominator for the percentage of successful injections is the number of attempted injections.

CONFIDENTIAL

205667

Example TAB_INJ2
 Protocol: MID205667
 Population: All Subjects (Safety)

Page 1 of 1

Table X.X
 Summary of Investigator Evaluation of User/Device Errors by Visit

Visit	n		Liquid Safety Syringe (N=XX)
WEEK 0	XX	Was the drug successfully injected?	
		Yes	XX (XX%)
		No	XX (XX%)
		Not attempted	XX (XX%)
		User Error	
		Any User Error	XX (XX%)
		Ring cap not removed from autoinjector	XX (XX%)
		Autoinjector not properly activated on injection site (e.g., gold needle guard not flush with skin)	XX (XX%)
		Autoinjector used upside down	XX (XX%)
		Autoinjector pulled away before end of injection (i.e., before purple indicator stopped moving)	XX (XX%)
		Other	XX (XX%)
		Device Error	
		Any Device Error	XX (XX%)
		Autoinjector leaking	XX (XX%)
		Components missing / broken / cracked	XX (XX%)
		Inspection window not clear	XX (XX%)
		Cannot remove ring cap	XX (XX%)
		Bent needle	XX (XX%)
		Cannot push the gold needle guard down to activate (i.e., force too high)	XX (XX%)
		Autoinjector does not activate (after pressing gold needle guard down)	XX (XX%)

Programming Note: Continue for Week 4 and 8

userid: /arenv/arprod/compound/study/final/drivers/drivername.sas DDMMYYYY HH:MM

Example TAB_INJ3
 Protocol: MID205667
 Population: All Subjects (Safety)

Table X.X
 Summary of Observer Checklist for In-Clinic Injections

Visit: WEEK 0

Liquid Safety Syringe
 (N=XX)

Time from removal of syringe from storage to injection (mins)	n	XX
	Mean	XX.X
	SD	XX.XX
	Median	XX.X
	Minimum	XX
	Maximum	XX
Confirm who will be administering the injection	n	XX
	Patient	XX (XX%)
	Caregiver	XX (XX%)
Subject/caregiver completed all the training required	n	XX
	Yes	XX (XX%)
	No	XX (XX%)
Subject/caregiver had instructions for use (IFU) available for review during injection (as recommended)	n	XX
	Yes	XX (XX%)
	No	XX (XX%)

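### The rule counting syringe-related dropouts as failures is written only for the primary endpoint, and a home dose followed by early withdrawal has no scheduled success verdict

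*SAP*

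**What the plan says.** **Denominators.** SAP 7.2, in line with protocol 9.4.1, bases each composite on subjects who attempted every component dose. For Weeks 4 and 8: "The denominator for the percentage calculation will be the number of subjects attempting an injection at both Week 4 and Week 8". For all three doses: "The denominator for the percentage calculation will be the number of subjects attempting all three doses at Week 0, 4 and 8". Footnote 1 of shell TAB_INJ1 (SAP 14.9) applies the same rule to every row: "The denominator for the percentage of successful injections is the number of attempted injections".

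**Failure rule for syringe-related withdrawal.** SAP 7.1 introduces it with "If there are withdrawals from study treatment due to issues pertaining to the use of the safety syringe". Missing results, and results recorded as not attempted, then count as unsuccessful in a sensitivity analysis. The scope given is the primary endpoint in 7.1, "sensitivity analysis of the primary endpoint will be performed, as described in Section 7.1" in 5.3, and "a sensitivity analysis of the primary analysis will be performed" in 14.5.2. The only link to the other endpoints is the opening of 7.2: "The following endpoints will be summarised in the same way as the primary endpoint (Section 7.1)". In the display list (SAP 14.8.2), Table 7.1 is the "Summary of the Proportion of Subjects Successfully Able to Self-Administer Injection by Visit"; none of Tables 7.1 to 7.5 is titled as a sensitivity analysis.

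**Schedule.** Protocol 4.1 says that the investigator judges every injection for success. In protocol 7.1, copied in SAP 14.1.1, the success-assessment row is marked at V2 and V4 only, and note p places the Week 4 home-dose judgement at V4. Notes n and o bring the diary and the home syringe back at Early Withdrawal, with inspection, when the last dose was taken at home.

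**The concern.** Stopping treatment means leaving the study (protocol 5.5), so a subject who stops attempts no later dose. The sponsor already treats a syringe-related stop as informative for the Week 8 rate. The same stop is just as informative for the Week 4 rate and the composites, yet the SAP does not clearly apply the rule there. Someone programming the tables could read 7.2 either way, and the display list does not settle it.

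For the composites there is a further group whose result is already known: subjects who failed a component dose and then stopped. They cannot have succeeded at both or all three doses, but they are left out of the row. The syringe rule, even if extended, would miss those who stopped for another reason.

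The schedule gap touches the secondary endpoint. A subject who takes the home dose and leaves before V4 has attempted a Week 4 injection and so belongs in that denominator, but no visit is marked for the verdict that feeds the numerator.

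**Working it through.** **The plan's own figure.** The exact (Clopper-Pearson) interval for 46/50 = 92% is 80.8 to 97.8. Protocol 9.2.2 prints 81, 98. All 11 rows of that table reproduce.

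**Whose composite result is already settled**
- Weeks 4 and 8: a Week 4 failure with no Week 8 attempt. A Week 0 failure who then stops does not settle this endpoint.
- Weeks 0, 4 and 8: a Week 0 or Week 4 failure who then stops.

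**Size in one trial.** From protocol 9.2.1: 55 enrolled, up to 10% dropout, 50 complete, so 5 stop. Assumed: 46 of the 50 completers succeed at every dose. Let k be the number of stoppers with a recorded failure of a component dose; the documents do not give k, so its range is 0 to 5. The planned row is 46/50 for every k; with known failures counted it is 46/(50 + k).

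| k | Rate | 95% CI |
|---|---|---|
| 0 | 46/50 = 92.0% | 80.8 to 97.8 |
| 1 | 46/51 = 90.2% | 78.6 to 96.7 |
| 3 | 46/53 = 86.8% | 74.7 to 94.5 |
| 5 | 46/55 = 83.6% | 71.2 to 92.2 |

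For Weeks 4 and 8, if 2 of the 5 stop after Week 4, k can only be 0, 1 or 2: 92.0%, 90.2% or 46/52 = 88.5%.

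**Size of the scope gap at Week 4.** Assumed: 3 subjects stop after Week 0 because of the syringe, and the other 52 all succeed at Week 4. The planned rate is 52/52 = 100% (93.2 to 100). With the failure rule it is 52/55 = 94.5% (84.9 to 98.9).

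**Expected bias of the composites.** Assumed: each dose succeeds independently with probability 0.95; at each of the two intervals a subject stops with probability s after a success and rs after a failure; overall stopping is 5/55. The chance of continuing through one interval is a = 1 − s(0.95 + 0.05r), with a² = 50/55, so a = 0.9535 and s = 0.0465/(0.95 + 0.05r).

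- Planned, Weeks 0, 4 and 8: 0.95³(1 − s)²/a². True value 0.95³ = 85.74%.
- Planned, Weeks 4 and 8: 0.95²(1 − s)/a. True value 0.95² = 90.25%.
- Counting known failures adds their expected share K to the denominator. For three doses the rate is 0.95³(1 − s)²/(a² + K), with K = 0.05rs + 0.05(1 − rs)(1 − a) + 0.95(1 − s)(0.05)rs. For two doses it is 0.95²a(1 − s)/(a² + K), with K = 0.05ars.

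| r | Three doses, planned | Three doses, known failures counted | Two doses, planned | Two doses, known failures counted |
|---|---|---|---|---|
| 1 | 85.7 | 85.1 | 90.25 | 90.0 |
| 2 | 86.1 | 85.1 | 90.5 | 90.0 |
| 5 | 87.1 | 85.2 | 91.0 | 90.1 |
| 10 | 88.4 | 85.3 | 91.6 | 90.1 |

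The planned rows run high by 0 to 2.6 points (88.35 − 85.74) and 0 to 1.4 points (91.62 − 90.25). The rows with known failures counted run slightly low throughout. The expected number of known failures among stoppers for three doses is 55K = 0.37, 0.58, 1.12 and 1.78 at r = 1, 2, 5 and 10.

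**Schedule gap.** If 2 subjects stop after the home dose, 52 have attempted Week 4 and 2 lack a scheduled verdict. If the 50 with a verdict all succeed, the rate prints as 50/52 = 96.2% (86.8 to 99.5) when the two stay in the denominator without a success, or 50/50 = 100% (92.9 to 100) when they are dropped. The SAP does not say which. The error can go either way, depending on whether those two injections worked.

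**The case against.** The attempt-based denominator is declared, is the same in protocol 9.4.1, SAP 7.2 and the TAB_INJ1 footnote, and matches the primary endpoint. Success among those who attempted the doses is a legitimate descriptive quantity in a study with no hypothesis test. TAB_INJ1 prints attempted n (%) on every row, so a change of denominator is visible. A failed injection still counts in its own single-dose row and appears in TAB_INJ2 and Listing 15. All of this stands, and it is why the planned rows should stay.

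A reader might infer that the composites are biased upward or misleading. With one Week 0 failure who stops and every other attempt successful, the table shows 54/55 = 98.2% for Week 0 beside 50/50 = 100% for all three doses. That judges the row against a denominator it does not claim. The documents do not support a finding of bias: it requires stopping to depend on failing, a failed injection is not a withdrawal criterion (protocol 5.5.1), and no figure links the two. The k = 3 and k = 5 rows are tails, since they need most or all stoppers to be failures.

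It can also be said that SAP 7.2 already carries the rule over, because 7.1 contains it, and that a conditional analysis need not have its own display. That reading is possible, but three sections name only the primary endpoint or primary analysis, so the scope is ambiguous at best.

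On the schedule, a reader might infer that the home-dose result is lost. That goes too far: protocol 4.1 and 7.3 require assessment, and the syringe is inspected at Early Withdrawal. What is missing is a scheduled place for the verdict.

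**Conclusion.** The point holds as two gaps of low impact. First, the sponsor's own failure rule for syringe-related withdrawal is not clearly extended to the secondary Week 4 endpoint or the composites, and the composite rows also omit subjects already known to have failed. Second, the schedule does not carry out protocol 4.1 for a home dose followed by withdrawal before V4.

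The effect is zero if no such subject exists, and the planned composites are unbiased under random dropout. Under the assumed model the upward bias is at most 2.6 points (three doses) and 1.4 points (Weeks 4 and 8), against an exact interval 17 points wide (80.8 to 97.8 for 46/50). In a single trial each known failure costs about 2 points. The 95% success rate, r, k and the timing of stops are assumptions; the documents give only the 55, the 50 and the 10%. The primary Week 8 analysis is not affected. The composites are descriptive endpoints, classed as Other in protocol section 3 and SAP 2.2. Both gaps are worth closing because the scope and the counting rule are better fixed before the data are seen.

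**What to change.** 1. State in SAP 5.3, 7.2 and 14.5.2 that the syringe-related failure-imputation sensitivity analysis also applies to the Week 4 and composite endpoints. In that display, count any recorded failure of a component dose as a composite failure, whatever the reason for stopping, and print beside it the number of stoppers whose status is unknown. List the display in SAP 14.8.2. Keep the planned rows as the main result and describe the sensitivity row as conservative (low-leaning). It is not the lowest possible cohort value, because stoppers of unknown status are left out. Do not print modelled percentages in the results table.
2. Mark the success assessment at Early Withdrawal when the last dose was the home dose, in both copies of the schedule (protocol 7.1 and SAP 14.1.1), so that they agree with protocol 4.1.

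**Cost.** A sentence in three SAP sections, one entry in the display list, a few table rows with a count, and one mark in each schedule. The second change alters the protocol, so it needs a minor amendment with the usual ethics review. The only new data item is the verdict itself, at a visit where the syringe is already inspected.
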